## 12. Follow-up

During the study period, each enrolled case was independently archived and registered for evaluation (CRF), and a resident physician was to be hired to be responsible for follow-up, registration, filling, and storage. After the end of treatment, the enrolled patients will be reviewed in the outpatient clinic in the first month after surgery, and then will be followed up regularly for 3-6 months until the death of the patient or the end of the study. The content of each review must include: thyroid function, parathyroid hormone level, thyroid ultrasonography. Questionnaires were conducted in the first and third months after surgery, and the scores of the Beauty Evaluation Scale and the Postoperative Scar Scale

were recorded and counted.

### 13. Study Start and Completion

Study Start: March 1, 2022

Anticipated Study Completion: June 30, 2023

A total of 40 patients in the RASSET group and 40 patients in the open group will be Enrolled, follow up 1 and 3 months after the operation, and the clinical data will be collected and analyzed statistically.

# Appendix

## Appendix 1 Cosmetic satisfaction questionnaire

Q1. How satisfied are you with your neck scar or a scarless neck?

Very satisfied(1) Satisfied(2) Average(3) Dissatisfied(4) Verydissatisfied(5)

Q2. How satisfied are you with the contour of your neck?

Very satisfied(1) Satisfied(2) Average(3) Dissatisfied(4) Verydissatisfied(5)

Q3. Do you think others look at your neck scar?

Absent (0) Sometimes (1) Frequent (2) Always (3)

Q4. Do you try to conceal your scar?

Absent (0) Sometimes (1) Frequent (2) Always (3)

Q5. Does your neck scar influence your choice of clothes?

Absent (0) Sometimes (1) Frequent (2) Always (3)

Q6. How often do you think about your scar?

Absent (0) Sometimes (1) Frequent (2) Always (3)

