## Study Protocol

### 1. Background

Thyroid cancer is one of the most common malignant tumors in the head and neck. Among it, papillary thyroid carcinoma accounts for about 70% of thyroid cancer. The degree of malignancy is low, but there is a tendency for multicentricity, and cervical lymph node metastasis occurs early. Due to the development of diagnosis technology, the amount of papillary microcarcinoma is getting higher and higher. At the same time, the change of aesthetic makes young women pursue a scarless neck.

Surgery is the first choice of treatments for early-stage thyroid cancer. Traditional open surgery tended to leave a long scar on the neck, which affects the cosmetic outcome. At present, many reported approaches, such as trans-areola approach, trans-axillary approach, trans-oral approach or some combined approaches, all have wider flap dissection or greater body trauma, and at the same time, these above approaches are difficult to achieve complete dissection of central lymph nodes.

Therefore, based on the experience of transauricular hairline endoscopic thyroidectomy, we established a new operative method-the Retro-auricular single-site endoscopic thyroidectomy (RASSET). The incision is only 3cm and located at the

posterior sulcus of the auricle, which can meet the cosmetic needs. Compared with other endoscopic approaches, the dissection area is small and the flap dissection is small, which may reduce the surgical trauma. The RASSET is easy to resect the upper pole of the thyroid gland, and can achieve complete dissection of the central lymph nodes. The article titled "A comparative study between retro - auricular single - site endoscopic thyroidectomy and transoral endoscopic thyroidectomy vestibular approach: a single - center retrospective analysis" has been published in "Chin J Surg". Guangdong Medical Information Research Institute recognized that there was no report of endoscopic thyroid surgery for this approach at home and abroad, and it also passed the new technology evaluation in the Sun Yat-sen University Cancer Center, and was recognized as an international leader.

**Figure 1. A:**Sun Yat-sen University Cancer Center Certificates(international innovation). **B:**Guangdong Medical Information Research Institute Certificates(no report of this approach).**C:**Zhonghua Wai Ke Za Zhi(a new approach).

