**Figure 2. [name]'s authorization**

### 3. Study Eligibility

- Inclusion Criteria:
  - Age 18-70 years old, no gender restrictions.
  - Fine-needle aspiration cytology(FNA) confirmed papillary thyroid carcinoma(PTC).
  - Early stage PTC (stage T1N0M0).
  - Preoperative ultrasonography showed unilateral glandular lobe malignant tumor and the largest diameter was not more than 2cm, without cervical lymph node metastasis and extensive metastasis.
  - Patients undergoing thyroid lobectomy and central lymph node dissection.
  - Patients who have signed an approved Informed Consent.
- Exclusion Criteria:

- Patients who do not accept case data collection for various reasons.
- The clinical data unfit this study (at the discretion of the investigator) .
- Patients who have undergone neck surgery or radiotherapy before this trial.
- Patients who have uncontrolled hyperthyroidism.
- Withdrawal criteria:
 

(A withdrawal case refers to a patient who withdraws from treatment for various reasons in study. Patients with the following conditions will be withdrawn from investigational treatment.)

  - The patient himself or his legal representative requests to withdraw.
  - In the opinion of the investigator, the patient's continued participation in the study will be detrimental to his health.
- Elimination Criteria:
  - Patients who violated the requirements of the research protocol.
  - The quality of data records is incomplete and inaccurate.
  - Lost cases.

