## 11. Statistical analysis

Professional statisticians undertake statistical analysis tasks and participate in the whole process from experimental design, implementation to analysis and summary. After the study protocol and case report form are completed, a statistical analysis plan shall be formulated. After some necessary modifications shall be made during the study process as required, and a statistical analysis report shall be provided after the data analysis is completed.

- Sample size

In this clinical study, the test level  $\alpha$  was set to be 0.05 on both sides. the test efficiency Power (ie,  $1-\beta$ ) was selected as 0.8 (ie, type II error  $\beta=0.2$ ). The sum standard deviation is  $5.54\pm 1.75$ , and the mean and standard deviation of the score of the cosmetic effect evaluation scale of the experimental group is expected to be  $3.92\pm 1.41$ . The 1:1 parallel control method is used, and the sample size calculation formula is based on the mean comparison of the two samples. According to the calculation of PASS software, this study requires a sample size of about 72 people (36 cases in each group). Considering the 10% dropout rate, the required sample size for each group is 40 cases, and a total of 80 cases in the two groups are required.

- Statistical Analysis

All analyses were performed using SPSS 26.0, and a P value less than 0.05 was considered significant. Normally distributed quantitative data are represented by mean (SD) [range]. Non-normally distributed quantitative data are represented by M (QR) . Comparison between groups was performed using the Mann-Whitney U test. Categorical data are expressed as frequencies and percentages. Comparisons between groups were performed using the  $\chi^2$  test or Fisher's exact test.

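### Do the two questionnaire items about a neck scar build an artificial advantage for RASSET into the primary endpoint?

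*Protocol*

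**What the plan says.** Appendix 1 has six items. Items 1 and 2 (satisfaction with the neck scar or with having none, and with neck contour) are scored 1 to 5. Items 3 to 6 are scored 0 (absent) to 3 (always), and a lower score is better. Items 3 and 5 name the neck: "Q3. Do you think others look at your neck scar" and "Q5. Does your neck scar influence your choice of clothes". Items 4 and 6 refer to the patient's scar without giving a site. Items 3 to 6 offer no not-applicable option.

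Section 1 places the 3 cm RASSET incision in the "posterior sulcus of the auricle, which can meet the cosmetic needs", and says that open surgery tends to leave a long neck scar that harms the cosmetic result. Section 7 makes the satisfaction score at 3 months the primary outcome and adds the Vancouver Scar Scale at 1 and 3 months. The developer's letter in section 2 says the questionnaire was built for thyroidectomy, remote-access approaches included, and permits use of the Chinese version. Among the elimination criteria in section 3 is "The quality of data records is incomplete and inaccurate".

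**The concern.** Read literally, items 3 and 5 do not ask about the scar that a RASSET patient has. She may answer 0 whatever she thinks of the scar behind her ear, or leave the item blank and risk elimination for an incomplete record. The two items carry up to 6 points, and the planned difference is only 1.62. If they sat at 0 in one arm for reasons unrelated to satisfaction, a positive primary result could reflect the position of the scar and not contentment with it, and blanks could be lost mainly from one arm. The trial is open-label and patients choose their operation, so neither blinding nor randomisation would offset this.

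**Working it through.** **Inputs.** From section 11: alpha "was set to be 0.05 on both sides"; power that "was selected as 0.8 (ie, type II error" 0.2); means and SDs 5.54 (1.75) and 3.92 (1.41); "The 1:1 parallel control method is used". The label of the first mean is garbled and is read here as the open group. Item ranges come from Appendix 1. That the total is a simple sum is an assumption.

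**The plan's own figure.** The difference is 5.54 - 3.92 = 1.62, and the pooled SD is √((1.75² + 1.41²)/2) = 1.589. With n = 2(z₀.₉₇₅ + z₀.₈₀)² × SD²/difference² = 7.849 × 5.0506/2.6244 = 15.1, the result is 16 per group (17 with the noncentral t). Section 11 states "this study requires a sample size of about 72 people (36 cases in each group"). The figure of 36 is what the formula gives for 99% power (18.37 × 1.9245 = 35.4). This mismatch is a separate matter and has no bearing on the wording of the items.

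**Score range.** Minimum 1 + 1 + 0 + 0 + 0 + 0 = 2; maximum 5 + 5 + 3 × 4 = 22. Items 3 and 5 hold 6 of the 20 points of span (30%).

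**Contribution of items 3 and 5.** Suppose RASSET patients score 0 on both and open patients average m on each. The contribution is 2m, its share 2m/1.62, and the remaining difference 1.62 - 2m. Power for that remainder at 36 per group is Φ(remainder/0.3746 - 1.96), where 0.3746 = 1.589 × √(2/36), if the SD does not change (assumption).

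| m (assumed) | 2m | share of 1.62 | remainder | power |
|---|---|---|---|---|
| 0.1 | 0.20 | 12% | 1.42 | 97% |
| 0.2 | 0.40 | 25% | 1.22 | 90% |
| 0.3 | 0.60 | 37% | 1.02 | 78% |
| 0.405 | 0.81 | 50% | 0.81 | 58% |
| 0.5 | 1.00 | 62% | 0.62 | 38% |
| 0.6 | 1.20 | 74% | 0.42 | 20% |

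At m = 0.8 the share is 1.6/1.62 = 99%. The two items supply more than half only if m exceeds 0.405. The protocol gives no item means, so it does not decide between the rows; all of them lie between absent and sometimes.

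**What the text supports.**

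- *Fixed at 0?* No scoring rule says so. Patients answer the items themselves and may have the ear scar in mind.
- *Artefact or effect?* Section 1 gives the neck scar as the drawback of open surgery and a scar-free neck as what patients seek. Being looked at because of a neck scar, or dressing around it, is what the operation is meant to spare them. An answer of absent is then a true value.
- *Right instrument?* The developer's letter says it covers remote-access surgery. Appendix 1 is in English while the letter permits the Chinese version, so the contrast between neck scar and scar may come from translation.
- *Is the RASSET scar left unmeasured?* No. Items 4 and 6 name no site, item 1 allows for a scarless neck, and the Vancouver Scar Scale rates scar quality at two visits.
- *Blanks?* The elimination criterion concerns the quality of records in general. Nothing says that one blank item removes a patient, the absent option is open to every patient, and open-surgery patients can leave blanks too.

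**The case for a change.** The strongest argument for the concern avoids guessing item means and uses the plan's own total. The open mean lies 5.54 - 2 = 3.54 above the floor. Spread equally over six items, items 3 and 5 carry 3.54 × 2/6 = 1.18 points (73% of 1.62); spread by item range, 3.54 × 6/20 = 1.06 (66%). The remainder of 0.44 to 0.56 would have only about 22-32% power at 36 per group. In addition, item 1 provides for a patient without a neck scar while items 3 and 5 do not, and this ambiguity falls almost wholly on one arm.

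The arithmetic stands as a possibility: the two items could supply most of the difference. An even spread is still an assumption, and so is an unchanged SD after two items are removed. More importantly, a large share would not show a fault. The planned means are read as totals on this scale, so whatever items 3 and 5 add is already inside the 1.62, and low power for a score without them matters only if that score were the endpoint. Removing them would take out part of the effect under study. The uneven wording is real, but a completion instruction or item-level results would be optional additions.

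**Conclusion.** The concern does not hold. The quotations and the 1.62-point difference are correct, but nothing in the protocol forces items 3 and 5 to 0, and a low score on them from a patient without a neck scar records the benefit that the trial is designed to compare, on a form described by its developer as suitable for remote-access surgery. The share of the planned difference carried by the two items runs from 12% to 99% for assumed open-arm item means of 0.1 to 0.8, given a simple-sum score and RASSET patients at 0; the protocol gives nothing that narrows this range. Loss of blanks from one arm only is conjecture. Rewording an authorised questionnaire, or making the conclusion depend on a total without these items, would be a debatable trade-off and not the correction of an error.

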## Appendix 2 Vancouver scar scale score

	Feature	Score
Vascularity	Normal	0
	Pink	1
	Red	2
	Purple	3
Pigmenta- tion	Normal	0
	Hypo-pigmentation	1
	Mixed-pigmentation	2
	Hyper-pigmentation	3
Pliability (Elasticity)	Normal	0
	Supple (flexible with minimal resistance)	1
	Yielding (giving way to pressure)	2
	Firm (inflexible, not easily moved, resistant to manual pressure)	3
	Banding (rope-like tissue that blanches with extension of the scar)	4
	Contracture (permanent shortening of scar, producing deformity or distortion)	5
Height	Flat	0
	< 2 mm	1
	2-5 mm	2
	> 5 mm	3
Pain	None	0
	Occasional	1
	Requires medication	2
Itchiness	None	0
	Occasional	1
	Requires medication	2

## Appendix 3 AJCC 8th Edition/TNM Classification System for

### Differentiated Thyroid Carcinoma

Staging flowchart for differentiated thyroid cancer (AJCC 8e)						
Age at diagnosis	M category	Gross ETE	Structures involved	Tumor size	N category	Stage
<55 years	M0	yes or no		any	any	I
	M1	yes or no		any	any	II
≥ 55 years	M0	no		≤ 4 cm (T1-2)	N0/Nx	I
				> 4 cm (T3a)	N1a/N1b	II
	yes		only strap muscle (T3b)	any	any	II
			s/cutaneous, larynx, trachea, esophagus, RL nerve (T4a)	any	any	III
			prevertebral fascia, encasing major vessels (T4b)	any	any	IVA
	M1	yes or no	any or none	any	any	IVB

TNM definitions (AJCC 8e)	
for papillary, follicular, poorly differentiated, Hürthle cell, medullary, and anaplastic thyroid carcinomas	
TX	Primary tumor cannot be assessed
T0	No evidence of primary tumor
T1	Tumor ≤ 2 cm in greatest dimension limited to the thyroid
T1a	Tumor ≤ 1 cm in greatest dimension limited to the thyroid
T1b	Tumor > 1 cm but ≤ 2 cm in greatest dimension limited to the thyroid
T2	Tumor > 2 cm but ≤ 4 cm in greatest dimension limited to the thyroid
T3*	Tumor > 4 cm limited to the thyroid or gross extrathyroidal extension invading only strap muscles
T3a*	Tumor > 4 cm limited to the thyroid
T3b*	Gross extrathyroidal extension invading only strap muscles (sternohyoid) from a tumor of any size
T4	Includes gross extrathyroidal extension into major neck structures
T4a	Gross extrathyroidal extension invading subcutaneous soft tissues, larynx, trachea, esophagus, or recurrent laryngeal nerve from a tumor of any size
T4b	Gross extrathyroidal extension invading prevertebral fascia or encasing carotid artery or mediastinal vessels from a tumor of any size
NX	Regional lymph nodes cannot be assessed
N0	No evidence of regional lymph nodes metastasis
N0a*	One or more cytologic or histologically confirmed benign lymph node
N0b*	No radiologic or clinical evidence of locoregional lymph node metastasis
N1*	Metastasis to regional nodes
N1a*	Metastasis to level VI or VII (pretracheal, paratracheal, or prelaryngeal/Delphian, or upper mediastinal) lymph nodes; this can be unilateral or bilateral disease
N1b*	Metastasis to unilateral, bilateral, or contralateral lateral neck lymph nodes (levels I, II, III, IV, or V) or retropharyngeal lymph nodes
M0	No distant metastasis
M1	Distant metastasis
* all categories may be subdivided as solitary tumor (s) and multifocal tumor (m) – the largest tumor determines the classification
